## CLINICAL TRIAL PROTOCOL SYNOPSIS

Name of company: Boehringer Ingelheim		Tabulated Trial Protocol			
Name of finished product: N.A.					
Name of active ingredient: Xentuzumab (BI 836845)					
Protocol date: 28 Mar 2014	Trial number: 1280.16		Revision date: 02 Nov 2016		
Title of trial: A phase Ib open-label clinical trial of once daily oral treatment of afatinib plus weekly intravenous infusion of Xentuzumab (BI 836845) in patients with EGFR mutant non-small cell lung cancer with progression following prior EGFR tyrosine kinase inhibitors					
Co-ordinating Investigator :   Phone: Fax:					
Trial sites: Multi-centre trial conducted in 4 countries (Korea, Taiwan, Singapore and Japan) Approximately 12 sites					
Clinical phase: Ib					
Objectives:  

Part A: To determine the Maximum Tolerated Dose (MTD) and/or Recommended Phase II Dose (RP2D) based on evaluation of safety and tolerability of Xentuzumab (BI 836845) when administered in combination with afatinib in patients with non-small cell lung cancer with progression following prior treatment (EGFR TKI or platinum-based chemotherapy)

Part B: To evaluate the early anti-tumour activity of Xentuzumab (BI 836845) in combination with afatinib in patients with EGFR mutant non-small cell lung cancer with progression following prior irreversible EGFR TKIs.

 Secondary objectives Part A and Part B:  

To evaluate the safety of Xentuzumab (BI 836845) in combination with afatinib in patients with non-small cell lung cancer

					

Proprietary confidential information.

© 2016 Boehringer Ingelheim International GmbH or one or more of its affiliated companies. All rights reserved.

This document may not - in full or in part - be passed on, reproduced, published or otherwise used without prior written permission.

Name of company: Boehringer Ingelheim		Tabulated Trial Protocol			
Name of finished product: N.A.					
Name of active ingredient: Xentuzumab (BI 836845)					
Protocol date: 28 Mar 2014	Trial number: 1280.16		Revision date: 02 Nov 2016		
Methodology: Open-label, 3+3 dose escalation (Part A) study of Xentuzumab (BI 836845) in combination with afatinib, followed by an expansion phase (Part B)					
No. of patients:					
total entered: Approximately 42 patients					
each treatment: Part A: Approximately 24 patients / Part B: Approximately 18 patients					
Diagnosis : Part A: Patients with pathologic confirmation of advanced and/or metastatic stage IIIb/IV non-small cell carcinoma of lung Part B: Patients with pathologic confirmation of advanced and/or metastatic stage IIIb/IV non-small cell carcinoma of lung who have failed at least one irreversible EGFR TKI therapy					

Proprietary confidential information.

© 2016 Boehringer Ingelheim International GmbH or one or more of its affiliated companies. All rights reserved.  
This document may not - in full or in part - be passed on, reproduced, published or otherwise used without prior written permission.

Name of company: Boehringer Ingelheim		Tabulated Trial Protocol		
Name of finished product: N.A.				
Name of active ingredient: Xentuzumab (BI 836845)				
Protocol date: 28 Mar 2014	Trial number: 1280.16		Revision date: 02 Nov 2016	
Main criteria for inclusion:  1. Patients with pathologic confirmation of advanced and/or metastatic stage IIIb/IV non-small cell carcinoma of lung 2. Documented activating EGFR mutation (exon 19 deletion, L858R, G719X, L861X). Exception: patient with squamous cell predominant histology in Part A 3. Presence of EGFR activating mutation and absence of EGFR T790M mutation in the tumour associated with the latest disease progression. Only applicable in Part B 4. Adequate fresh or archival tumour tissue at the latest disease progression immediately prior to the study entry must be made available for central EGFR mutation test and/or resistance analysis 5. Part A: Progression of disease ( RECIST v1.1 ) while on continuous treatment with single agent EGFR TKI (e.g. erlotinib or gefitinib or afatinib) or for histology other than adenocarcinoma and without prior EGFR TKI treatment: progression of disease (RECIST v1.1) on platinum-based chemotherapy. Part B: Progression of disease (RECIST v1.1) while on continuous treatment with single agent of the second generation irreversible EGFR TKI (e.g. afatinib or dacomitinib) Note: In both parts, patients whose disease progresses only in the central nervous system (CNS) are not eligible 6. No intervening systemic therapy between cessation of EGFR TKI and initiation of the treatment in the study. Exception: patient with squamous cell predominant histology in Part A 7. Patients must have measurable disease per RECIST v1.1 ( R09-0262 - Appendix 10.5 ) presented after tumour biopsy for the latest disease progression 8. Recovered from any previous therapy related toxicity to ≤ Grade 1 at study entry (except for stable sensory neuropathy ≤Grade 2 and alopecia)				
Test product(s): Xentuzumab (BI 836845) in combination with afatinib dose: Xentuzumab (BI 836845) 1000 mg with 30 mg afatinib (starting dose level) mode of admin.: Xentuzumab (BI 836845): Intravenous infusion over 60 minutes/ afatinib: Once daily oral dosing				
Comparator products: NA dose: NA mode of admin.: NA				

Proprietary confidential information.

© 2016 Boehringer Ingelheim International GmbH or one or more of its affiliated companies. All rights reserved.

This document may not - in full or in part - be passed on, reproduced, published or otherwise used without prior written permission.

Name of company: Boehringer Ingelheim		Tabulated Trial Protocol		
Name of finished product: N.A.				
Name of active ingredient: Xentuzumab (BI 836845)				
Protocol date: 28 Mar 2014	Trial number: 1280.16		Revision date: 02 Nov 2016	
Duration of treatment: Continuous treatment until disease progression, intolerable adverse events (AEs), consent withdrawal or non-compliance with the study protocol				
Criteria for efficacy: Primary endpoint (for Part B) 

• Objective response (OR), defined as complete response (CR) or partial response (PR) according to RECIST v1.1

 Secondary endpoints (for Part B) 

• Disease control, defined as complete response (CR), partial response (PR) or stable disease (SD)

• Time to objective response, defined as the duration of time from the date of first treatment administration until objective response

• Duration of objective response, defined as the duration of time from objective response to the date of first objective tumour progression or death due to any cause

				
Criteria for safety: 

• MTD of Xentuzumab (BI 836845) in combination with afatinib (primary endpoint for Part A only)

• Dose limiting toxicity (DLT) during the first treatment course (primary endpoint for Part A only)

• Adverse Events (AEs) according to Common Terminology Criteria (CTCAE version 4.03), physical examination, vital signs, ECOG performance score, safety laboratory parameters, electrocardiogram (ECG), and Left Ventricular Ejection Fraction (LEVF)

				
Statistical methods: Descriptive and exploratory analyses				

Proprietary confidential information.

© 2016 Boehringer Ingelheim International GmbH or one or more of its affiliated companies. All rights reserved.

This document may not - in full or in part - be passed on, reproduced, published or otherwise used without prior written permission.

## FLOW CHART

Refer to Part A and Part B

Study Periods	Screening	Treatment courses**								FU ***	OP *****	
		SCR *	Course 1				Course 2 Onwards					
Visit		1	2	3	4	1	2	3	4	EOT ***	FU1	FU2
Days	-42 to -1	1	8	15	22	1	8	15	22		-	FUn
Informed consent 	X											
Demographics	X											
Medical history	X											
In- /Exclusion criteria (eligibility)	X 	X 										
Physical examination 	X	X							X		X	
Body height	X											
ECOG performance score	X	X						X		X	X	
Vital signs 	X	X	X	X	X	X	X	X	X	X	X	
Body weight	X	X							X		X	X
12 lead -ECG 	X	X		X								X
Left ventricular ejection fraction 	X											
Safety lab parameters 	X	X	X	X	X	X	X			X	X	
Urinalysis 	X							X				
Pregnancy test	X										X	
Adverse events	X	X	X	X	X	X	X	X	X	X	X	X 
Concomitant therapy	X	X	X	X	X	X	X	X	X	X	X 	
Tumour assessment by RECIST v1.1 	X								X			X
Tumour biopsy 	X										X 	
Medication diary card dispense 		X	X	X	X					X		
Afatinib compliance check			X	X	X	X	X	X	X	X		
BI836845 i.v. administration weekly		X	X	X	X	X	X	X	X			
Afatinib administration daily 							Continuous daily administration.					

Proprietary confidential information.

© 2016 Boehringer Ingelheim International GmbH or one or more of its affiliated companies. All rights reserved.

This document may not - in full or in part - be passed on, reproduced, published or otherwise used without prior written permission.

Study Periods	Screening	Treatment courses**										FU ****	OP *****
		Course 1				Couse 2 Onwards							
Visit	SCR *	1	2	3	4	1	2	3	4	EOT ***	FU1	FU2 – FUN	OP *****
Days	-42 to -1	1	8 (±2)	15 (±2)	22 (±2)	1	8 (±2)	15 (±2)	22 (±2)				Every 90 (±15)
Dispense afatinib		X				X							
Termination of trial medication											X		
Conclusion of Patient Participation 											X		X
Patient status (Part B)													X 

\*Screening visit should be performed within 42 days prior to first drug administration. Safety lab at the screening assessment can serve as the C1/V1 assessment if performed within 72 hours before the first treatment and does not need to be repeated.

\*\* A treatment course consists of 28 days and will be repeated until tumour progression (according to [RECIST v1.1](#)) confirmed by tumour imaging.

\*\*\* End Of Treatment (EOT) visit must be performed within 14 days of the last administration of study drug, i.e. both Xentuzumab (BI 836845) and afatinib. If last administration of the study drug occurs during a scheduled visit, examinations as defined for EOT should be performed instead of examinations for the scheduled visit.

\*\*\*\*First Follow-up (FU) visit 42 calendar days (up to +7 days) after the last administration of study drug for all patients (part A and part B). Additional FU visits (only for patients who discontinue not due to progressive disease) at 8-week intervals until progression, lost to follow-up or initiation of other anti-cancer treatment.

\*\*\*\*\* Observation period only for part B. For details see [Section 6.2.3.3](#).

Written informed consent must be obtained before any trial specific screening assessments are performed.

In/Exclusion criteria must be checked at screening and ensured before study medication has been firstly administered.

 Physical examination: includes cardiopulmonary examination, examination of the regional lymph nodes, and examination of the abdomen and an assessment of the mental and neurological status.

Vital signs: include pulse, temperature and blood pressure.

 ECG to be performed at Screening/ pre-infusion, during infusion (after 30±5 mins) and immediately prior to the end of the infusion (-10 mins) on Day 1 of Course 1/ a single ECG to be taken on Day 15 of Course 1/ thereafter a single ECG to be taken pre-infusion at the start of every course on Day 1, and also at EOTV.

MUGA scan or echocardiogram not older than 28 days prior to start of treatment. Further scans may be performed post treatment if clinically indicated

Haematology, biochemistry and coagulation parameters. Safety labs may be collected up to two days prior to the scheduled time points. Safety lab result at course 1 visit 1 should be reviewed by investigator before first administration of study medications. From course 2 onwards, safety lab assessment will be done at visit 1 and 3 of each course. For details see [Section 5.2.3](#).

Urinalysis (Dipstick).

 For observation period (after the patient completed last follow-up and when progression occurred or when new anti-cancer therapy started), the investigator may report SAE if she/he becomes aware of and considers relevant.

During Follow-up, concomitant therapy only needs to be recorded if indicated for the treatment of an AE.

Tumour assessment will be performed every 4 weeks after start of treatment with Xentuzumab (BI 836845) and afatinib for first 8 weeks (prior to courses 2 and 3 ), in 8-week intervals thereafter (e.g. prior to courses 5, 7, 9, etc.) and in 12-week interval after course 16 until PD or start of further anti-cancer treatment. It should include CT scans or MRI. CT images not older than 30 days at start of treatment will suffice as screening images and don't have to be repeated. The EOT tumour assessment is optional if performed in the previous 4 weeks. Imaging may be performed within 7 days of scheduled time point. Additional imaging follow up will be required for patients who discontinued not due to progressive disease at 8-week intervals until progression, lost to follow-up or initiation of other anti-cancer treatment.

Tissue biopsies to determine EGFR mutations and other relevant pathways at study entry and following progression may be obtained after obtaining informed consent. (Optional at the time of progression) In case there is a documented result of EGFR mutations available before study entry for Part A, local result is acceptable. For Part B, tumour sample provision to central laboratory is mandatory for confirmation of the result. Prior to any biopsy, patients must have controlled hematology parameters (INR and PTT within normal range) and platelet count ( $\geq 100,000 / \mu\text{L}$ ). See [Section 4.2.2](#) for restriction of

Proprietary confidential information.

© 2016 Boehringer Ingelheim International GmbH or one or more of its affiliated companies. All rights reserved.

This document may not - in full or in part - be passed on, reproduced, published or otherwise used without prior written permission.

antiplatelet and anticoagulant medications. For tissue biopsy at the time of progression after study treatments, separate informed consent must be obtained.

Part A: afatinib intake starting from Course 1 Day 8 up to Course 2 Day 1 and Course 3 Day 1 must be recorded in the patient diary and it should be dispensed to the patient on Day 1, 8, 15 and 22 of Course 1 and Day 22 of Course 2.  
Part B: afatinib intake from Course 2 Day 1 and Course 3 Day 1 must be recorded in the patient diary and the diary card should be dispensed to patient on Day 22 of Course 1 and Day 22 of Course 2.  
Completed diary card should be returned from the patient at next visit.

Afatinib treatment oral continuous daily administration. Patients should take the study medication at the same time every day to ensure a dose interval of approximately 24 hours.

Refer to [Section 6.2.3](#).

 All patients in Part B will be followed-up for overall survival at 3 monthly intervals (90±15 days) after the last follow-up visit. For details see Section 6.2.3.

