Patients are enrolled in the study once the informed consent form is signed. The screening period will be up to 6 weeks (42 days) during which time the eligibility will be confirmed. In order to meet the eligibility criteria regarding EGFR genotypes and/or to characterize resistance mechanisms, all patients need to provide archived tumour sample which is associated with EGFR TKI (or other treatment in EGFR wild type) resistance or undergo a fresh tumour biopsy. In the Part B, the EGFR genotypes must be confirmed by the authorized central laboratory. The eligibility criteria will be reconfirmed prior to the first administration of study medications. Eligible patients will be treated continuously with the study regimen in the absence of disease progression, intolerable adverse events, or other reason necessitating withdrawal (refer to [Section 3.3.4](#)). The treatment will be administered as courses of 28 days. Continued treatment beyond disease progression will not be allowed in the study.

All patients will have regular assessment of safety parameters as detailed in the [Flow Chart](#).

Tumour assessment by imaging according to [RECIST version 1.1](#) will be conducted at baseline and at fixed time points as specified in the Flow Chart.

An End of Treatment (EOT) visit is to be completed when a patient permanently discontinues both study drugs, for any reason listed in Section 3.3.4.

[figure not shown]
Proprietary confidential information.

© 2016 Boehringer Ingelheim International GmbH or one or more of its affiliated companies. All rights reserved.

This document may not - in full or in part - be passed on, reproduced, published or otherwise used without prior written permission.

The assessments required are listed in the [Flow Chart](#). Patients who permanently discontinue both study drugs due to other reason than progressive disease will continue to have tumour assessments according to the Flow Chart until disease progression, lost to follow-up or initiation of other anti-tumour therapy, whichever occurs first.

A Follow-up visit (FU1) will be completed 42 (+ 7) days after the last administration of study drug. Refer to the Flow Chart and Figure 3.1: 1 below for details. FU1 will be defined as the end of on-treatment period for this trial. After disease progression, patients will be monitored for vital status in the observation period (**for Part B only**).

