#### 5.2.2.2 Adverse event and serious adverse event reporting

All adverse events, serious and non-serious, occurring during the course of the clinical trial (i.e., from signing the informed consent onwards through the end of the follow-up period)

Proprietary confidential information.

© 2016 Boehringer Ingelheim International GmbH or one or more of its affiliated companies. All rights reserved.

This document may not - in full or in part - be passed on, reproduced, published or otherwise used without prior written permission.

will be collected, documented and reported to the sponsor by the investigator on the appropriate CRF(s) / eCRFs / SAE reporting forms. Reporting will be done according to the specific definitions and instructions detailed in the ‘Adverse Event Reporting’ section of the Investigator Site File.

For each adverse event, the investigator will provide the onset date, end date, intensity, treatment required, outcome, seriousness, and action taken with the investigational drug. The investigator will determine the relationship of the investigational drug to all AEs as defined in [Section 5.2.2.1](#).

The residual effect period (REP) for Xentuzumab (BI 836845) is 42 days. Therefore all events reported within 42 days after the last trial medication will be considered on treatment. All adverse events will be reported up until last follow up visit. The investigator does not need to actively monitor patients for adverse events during the observation period or once the clinical trial has ended. However, if the investigator becomes aware of an SAE(s) that occurred during the observation period or after the patient has completed the clinical trial, it should be reported by the investigator to the sponsor if considered relevant by the investigator, see Table 5.2.2.2:1.

Table 5.2.2.2: 1 AE/SAE reporting requirements

Time period	Reporting requirements
From signing of informed consent until last follow up visit (including 42 days after last trial drug administration and beyond if required)	Report all AEs and SAEs regardless of relatedness or whether the trial drug was administered. This includes all deaths.

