### 6.2.3.2 Follow-up

The residual effect period (REP) for Xentuzumab (BI 836845) is 42 days. Therefore all events reported within 42 days after permanent discontinuation of trial medication will be considered as 'on treatment'. At the end of REP, the first follow-up visit (FU1) is to be performed.

All patients should have a follow-up visit 42 days (+ 7 days) after permanent discontinuation of study drugs. At this follow-up visit, an end of trial assessment will be performed and documented in the e-CRF.

Additional follow-up visits at 8-week intervals should be performed for patients who are not progressed or new anti-cancer treatment has not been started according to the Flow Chart.

Follow-up period for every patient will end at the earliest of the following events:

- Lost to follow-up
- Disease progression
- Initiation of a new anti-cancer therapy
- Death
- End of whole trial as specified in [Section 6.2.3.5](#)

The following will be obtained and/or performed during the follow-up visits.

- Record any new AEs or SAEs and follow-up of ongoing adverse events
- Concomitant medications for treatment of an adverse event including trade name, indication and dates of administration
- Tumour assessment and imaging will be performed if applicable.
- Treatment and date with any other anti-cancer drug and/or best supportive care including the name and type of the anti-cancer drug
- Outcome (date of and reason for death, in case the patient had PD the actual date of PD will be recorded)

Follow-up of patients with AEs which have not recovered at the last planned follow-up visit, please refer to [Section 5.2.2.2](#).

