#### 7.3.3 Safety analyses

The occurrence of dose limiting toxicity (DLT) as well as the incidence, intensity, duration and causality of adverse events graded according to CTCAE Version 4.03 ([R10-4848](#)), laboratory parameters and vital signs will be evaluated in both parts of the study.

AEs will be evaluated using the CTCAE grading scheme. The overall incidence and intensity of adverse events, as well as their relatedness to the study medication will be reported for all treatment arms and combinations. Serious adverse events and events leading to dose reduction or treatment discontinuation will be tabulated. Descriptive statistics will be used to describe changes in laboratory parameters over time. In addition, all abnormalities of potential clinical relevance will be reported.

AEs that started within the period starting with first administration of the trial drug and ending 42 days after permanent discontinuation of study drugs (both Xentuzumab (BI 836845) and afatinib) will be considered as having occurred during 'on treatment'. Later events will be attributed to the post-treatment period and events occurring between IC date and first drug intake will be presented separately.

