6 GENERAL ANALYSIS DEFINITIONS

6.1 TREATMENTS

Part A and part B: Patients will be analysed according to the cohort initially assigned. All planned analysis will be presented by this cohort, unless specified otherwise. Handling of patients where cohort assignment has not been followed will be handled on a case-by-case basis, to be agreed at report planning meetings or DBL meeting (but prior to database lock).

For safety summaries data recorded during the Residual Effect Period (REP) will be considered as on-treatment. For this trial, the length of the REP is 42 days.

The actual study periods and treatment codes are defined in a document entitled “8-07-other-sdtm-trial-arms-trial-elements”, which can be found in Data Management and Statistics (DMS) folder, Section 8, within BIRDS.

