7.8.1 Adverse events

The analyses of AEs will be descriptive in nature. All analyses will be based on the number of patients with AEs (not the number of AEs).

For analysis multiple AE occurrence data on the CRF will be collapsed into an AE event provided that all of the following applies:

- All AE attributes are identical (Lowest Level Term (LLT), Common Terminology Criteria for Adverse Events (CTCAE) grade, action taken with trial medication, therapy required, seriousness, reason for seriousness, relationship, outcome, AE of special interest)
- The occurrences were time-overlapping or time-adjacent (time-adjacency of 2 occurrences is given if the second occurrence started on the same day or on the day after the end of the first occurrence)

For further details on summarisation of AE data, please refer to (2) and (4).

Adverse events will be coded with the most recent version of MedDRA. The severity of AEs will be scaled according to CTCAE (CTCAE version 4.03 (10)).

The analyses of adverse events will be based on the concept of treatment-emergent adverse events. That means that all adverse events with an onset between first treatment administration until end of the REP will be assigned as 'on treatment'. All adverse events occurring before first drug intake will be assigned to 'screening' and all adverse events occurring after the residual effect period will be assigned to 'post-treatment'; these AEs will be displayed in listings only. Adverse events will be displayed by the initial dose of study medication administered on the first day of treatment .

An overall summary of adverse events will be presented. The frequency of patients with adverse events will be summarised by treatment, primary system organ class and preferred term.

Separate tables will be provided for patients with drug-related adverse events, adverse events leading to dose reduction, adverse events leading to discontinuation, serious adverse events, serious drug-related serious adverse events, adverse events leading to death, other significant adverse events, adverse events of special interest, and adverse events fulfilling the DLT definition (for part A only), and drug-related adverse events leading to discontinuation.

Sorting order:

In tables presenting System Organ Classes (SOCs) and Preferred Terms (PTs), SOCs will be sorted alphabetically and PTs (within SOC) by descending frequency.

Reporting of CTCAE grades in tables:

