7.8.2 Laboratory data

7.8.2.1 Laboratory data

The analyses of laboratory data will be descriptive in nature and will be based on BI standards (5). The same on-treatment periods as considered for the analysis of adverse events will be applied for laboratory values except for that the baseline laboratory value will be included in the 'on-treatment' period. Patients having at least one post-baseline laboratory value will be displayed in the descriptive analyses.

Descriptive statistics, including change from baseline and frequency of patients with transitions relative to the reference range, will be provided. CTCAE grades for applicable laboratory parameters will be calculated according to CTCAE version 4.03 (10). The following outputs will be presented:

- Worst CTCAE grade experienced during the on-treatment phase.
- Transitions of CTCAE grade from baseline to worst laboratory value, from worst to last laboratory value during the on-treatment phase, and from baseline to last laboratory value.

Patients with missing CTCAE grade at baseline or no baseline value but post baseline values will be displayed in the category "Missing CTCAE grade at baseline". Laboratory values without CTCAE grading will be compared to their reference ranges and frequency tables will be provided for the number of patients within and outside the reference range at baseline and the last measurement on treatment.

Analysis of potentially clinically significant abnormal laboratory values, and handling of CTCAE grade -1 and -9 laboratory parameters, are described in the SOP for "Display and analysis of laboratory data" (5), Reference Document 9.

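### The 42-day on-treatment window has no visible cut or flag when the next anti-cancer therapy starts inside it, so all-causality safety tables can mix in next-line events

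*Protocol*

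**What the plan says.** The residual effect period (REP) is fixed in SAP 6.1: "For this trial, the length of the REP is 42 days". The on-treatment rule is then stated in several places:

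- Protocol 5.2.2.2: "Therefore all events reported within 42 days after the last trial medication will be considered on treatment". Protocol 6.2.3.2 repeats this in similar terms.
- Protocol 7.3.3 defines the period as "ending 42 days after permanent discontinuation of study drugs (both Xentuzumab (BI 836845) and afatinib) will be considered as having occurred during 'on treatment".
- SAP 7.8.1: "all adverse events with an onset between first treatment administration until end of the REP will be assigned as 'on treatment".
- SAP 7.8.2.1, for laboratory data: "The same on-treatment periods as considered for the analysis of adverse events will be applied for laboratory values", with the baseline value added.

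The Flow Chart places the closing visit, FU1, in every patient: "First Follow-up (FU) visit 42 calendar days (up to +7 days) after the last administration of study drug for all patients". That note sets only the visit date; the analysis rule is in the sections listed above. Protocol 3.1 gives a slightly different end point: "FU1 will be defined as the end of on-treatment period for this trial".

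The information needed to identify the next therapy is collected at follow-up visits (Protocol 6.2.3.2): "Treatment and date with any other anti-cancer drug and/or best supportive care including the name and type of the anti-cancer drug".

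**The concern.** Treatment beyond progression is not allowed (Protocol 3.1), so many patients will stop study drug at the point where another regimen is the natural next step. If that regimen starts within six weeks, its adverse events have onset inside a window labelled on-treatment. There is no control arm, and safety of the combination is the secondary objective of both parts (Protocol 2.2.2). A reader of an all-causality table then has no means of telling which on-treatment events arose after the patient had moved to another drug.

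For efficacy, the SAP does draw this line. Best overall response (SAP 5.1.2) and duration of response (SAP Table 5.2.2.2: 1) both stop at subsequent anti-cancer therapy. No matching rule is visible for safety.

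**Working it through.** The plan states no figure to reproduce. The check is a comparison of rules, followed by two small calculations.

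**1. Can the next therapy start inside the window?** Yes. Protocol 4.2.2.1 bars other anti-cancer therapy only alongside study treatment. The date-imputation table in SAP 6.6 allows a next-line start one day after the study drug stop date. The same table says that this imputation is needed only for PFS censoring.

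**2. Are events in that interval collected?** Probably, but the text conflicts.

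- For collection: FU1 is required in all patients (Flow Chart, Protocol 6.2.3.2). Protocol Table 5.2.2.2: 1 asks for all events regardless of relatedness to the last follow-up visit, the 42 days included. Protocol 6.1 collects events to the last follow-up visit. Protocol 6.2.3.3 starts the observation period only after FU1 for patients who progressed on treatment.
- Against: the text of Protocol 5.2.2.2 collects events to the end of the follow-up period, and Protocol 6.2.3.2 ends that period at the earliest of several events, including progression and a new anti-cancer therapy. Read literally, collection could stop before day 42.

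**3. Which outputs have no relatedness filter?** In SAP 7.8.1, the all-causality adverse event and serious event tables by CTCAE grade, and the table of on-treatment fatal events. In SAP 7.8.2, the worst on-treatment laboratory grade and the potential Hy's law cases.

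**4. How exposed are the laboratory outputs?** Less than the event tables. The Flow Chart (its table is partly broken in the text) appears to schedule post-treatment safety laboratory tests only at the end-of-treatment visit, within 14 days of last dose, and at FU1, on day 42 to 49. Under a 42-day REP, an FU1 sample on days 43 to 49 falls outside. In-window values are mainly the end-of-treatment sample, an FU1 sample exactly on day 42, and unscheduled tests, which Protocol 5.2.3 records in the eCRF.

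**5. Is 42 days itself unreasonable?** No. Protocol 1.2.1 gives a xentuzumab terminal half-life of about 6 days. 42 / 6 = 7 half-lives, and 0.5^7 = 0.8% remaining. The documents do not derive the REP this way, but its length is consistent with their own half-life.

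**6. How much of the window could be next-line time?** Let T be days on study treatment and s the days from last dose to next-line start. Both are assumptions, since the documents give neither. The share of the on-treatment window spent after next-line start is (42 − s) / (T + 42).

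| T | s | Calculation | Share |
|---|---|---|---|
| 28 | 1 | 41 / 70 | 59% |
| 56 | 1 | 41 / 98 | 42% |
| 56 | 7 | 35 / 98 | 36% |
| 56 | 14 | 28 / 98 | 29% |
| 56 | 28 | 14 / 98 | 14% |
| 168 | 28 | 14 / 210 | 7% |

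These are shares of time in a patient who does start another therapy. They are not event rates.

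**7. What does one patient weigh?** Part B plans 18 patients: 1 / 18 = 5.6 percentage points. SAP 7.8.1 counts patients, not events, so someone who already had that type of event earlier adds nothing to its incidence.

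**The case against.** The strongest reply is that on-treatment is a time window and not an attribution. A reader might infer that next-line toxicity is reported as toxicity of xentuzumab plus afatinib. The documents do not support that. The investigator judges the relationship of every event to study drug (Protocol 5.2.2.1, 5.2.2.2), and SAP 7.8.1 plans separate drug-related tables. This part of the reply stands, and it confines the problem to the all-causality and laboratory outputs.

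A reader might also infer that dose finding is compromised. It is not: a DLT must be drug-related, and the MTD uses only the first course (Protocol 5.2.6, 5.2.7). The RP2D has already been set (Protocol 4.1.3.2), Part B has no formal safety endpoints (5.2.1.2), and there are no formal tests (7.2).

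Keeping every event for seven half-lives is the cautious choice in an uncontrolled combination study, and a hard cut would move genuine delayed toxicity out of the main table. That also stands, and argues for showing both windows. Liver cases receive some attribution as well: the work-up in Protocol Appendix 10.6.2 takes a concomitant-drug history if imaging gives no cause, and SAP 7.8.2.2 flags true DILI cases.

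Finally, SAP 6.1 refers to a study-period document, and SAP 7.8 to internal standards, that are not in the public text. Handling may be specified there, so the point is about what is visible. None of this supplies a cut or flag in the rules as written.

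**Conclusion.** The gap is real and modest. Followed as written, the rules place events that begin on the next anti-cancer therapy, within 42 days of last study drug, in the all-causality on-treatment adverse event, serious event and fatal-event tables. The worst-grade and potential Hy's law laboratory outputs are exposed to a lesser extent. This assumes that such events are collected through FU1, which most of the protocol text supports and its list of events ending follow-up contradicts.

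The direction is known: for any given event, adding time after next-line start can only raise or leave unchanged the number of patients counted. The size is not. A reader might be tempted to put a range of percentage points on it, but the documents give no time to next therapy, no share of patients starting one within 42 days and no event rate on it. Any such range would rest on free choices and would have to allow for patients who already had the event. All that can be said is that each newly counted patient among 18 is 5.6 points; in the by-starting-dose columns of SAP section 7 the denominators can be smaller.

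**What to change.** In SAP 6.1, 7.8.1 and 7.8.2.1, derive for each patient the earlier of (a) last administration plus 42 days and (b) the day before the recorded start of subsequent anti-cancer therapy. Present the on-treatment adverse event and laboratory summaries to that date beside those for the full 42-day window. Show events and values after next-line start but within 42 days separately, with drug-related events flagged. Extend the use of the imputed next-line start date in SAP 6.6 beyond PFS censoring.

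Two sets of protocol text also need reconciling:

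- Section 5.2.2.2 (collection to the end of follow-up) and the list in 6.2.3.2 (follow-up ends at progression or new therapy), against FU1 for all patients and Table 5.2.2.2: 1.
- Section 3.1 (on-treatment ends at FU1, day 42 to 49), against the 42-day REP used elsewhere.

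The cost is one derived date from data already collected, one extra set of tables and some wording. The small downside is that delayed study-drug effects appearing after next-line start must be read from the separate display or the full-window table.
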